7.2.4 Day 7 Visit

During the Day 7 Visit, (Duration: ~2 hours) participants will:

1. Arrive at the Center at 9:00 AM after having abstained from smoking overnight.
2. Perform a CO breath assessment and concomitant medication review.
3. Have their overnight smoking abstinence (10-hours) verified by a CO measurement of 50% of Intake visit's CO value
4. Be asked questions about use of marijuana, other tobacco products (besides cigarettes), or vaping of any substance including tobacco/nicotine or other drugs in the past month.
5. Complete questionnaires:
 - Adverse Events Form (Open-Ended AEs)
6. Be introduced to and briefly practice the Relative Reinforcing Value of IQOS (RRVI) computerized lab task.
7. Complete computerized lab task: Relative Reinforcing Value of IQOS (RRVI).
8. Complete a standardized one-hour wait period in the laboratory, then complete required IQOS use in the lab.
9. Review instructions for IQOS use with a member of the research staff.
10. Receive an IQOS 3.0 holder and charger, a 7-day supply of regular and/or menthol HeatSticks, and 14 date-stamped zipped baggies for daily collection of spent filters and HeatSticks (7 for spent cigarette filters, 7 for used HeatSticks).
11. Be provided with instructions to switch completely from smoking combustible cigarettes to using IQOS.
12. Review written instructions for the collection and storage of used tobacco HeatSticks with a member of the research staff.

7.2.5 Day 11 Visit

During the Day 11 Visit (duration: ~30 min), participants will:

1. Perform a CO breath assessment and concomitant medication review.
2. Be asked questions about use of marijuana, other tobacco products (besides cigarettes), or vaping of any substance including tobacco/nicotine or other drugs in the past month.
3. Complete questionnaires:
 - Adverse Events Form (Open-Ended AEs)
4. Return used HeatSticks (and cigarette filters, if applicable) in date-stamped zipped baggies provided by the research staff.

7.2.6 Day 14 Visit

During the Day 14 visit (duration: ~30 min) participants will:

1. Perform a CO breath assessment and concomitant medication review.

CONFIDENTIAL

This material is the property of the University of Pennsylvania. Do not disclose or use except as authorized in writing by the study sponsor

2. Be asked questions about use of marijuana, other tobacco products (besides cigarettes), or vaping of any substance including tobacco/nicotine or other drugs in the past month.
3. Complete questionnaires:
 - Adverse Events Form (Open-Ended AEs)
4. Return used HeatSticks (and cigarette filters, if applicable) in date-stamped zipped baggies provided by the research staff.
5. Receive second seven-day supply of HeatSticks, and 14 date-stamped zipped baggies for daily collection of spent filters and HeatSticks (7 for spent cigarette filters, 7 for used HeatSticks).

7.2.7 Day 17 Visit

During the Day 17 visit (duration: ~30 min) participants will:

1. Perform a CO breath assessment and concomitant medication review.
2. Be asked questions about use of marijuana, other tobacco products (besides cigarettes), or vaping of any substance including tobacco/nicotine or other drugs in the past month.
3. Complete questionnaires:
 - Adverse Events Form (Open-Ended AEs)
4. Return used HeatSticks (and cigarette filters, if applicable) in date-stamped zipped baggies provided by the research staff.

7.2.8 Day 21 Visit

During the Day 21 visit (duration: ~30 min) participants will:

1. Perform a CO breath assessment and concomitant medication review.
2. Be asked questions about use of marijuana, other tobacco products (besides cigarettes), or vaping of any substance including tobacco/nicotine or other drugs in the past month.
3. Complete questionnaires:
 - Adverse Events Form (Open-Ended AEs)
4. Return used HeatSticks (and cigarette filters, if applicable) in date-stamped zipped baggies provided by the research staff.

7.2.9 Day 22 Visit

During the Day 22 visit (Duration: ~30 min) participants will:

1. Complete questionnaires:
 - Adverse Events Form (Open-Ended AEs)
 - Concomitant medication review
 - Changes in motivation to quit smoking (Contemplation Ladder)
2. Return all remaining used HeatSticks and spent cigarette filters
3. Be informed of the lack of data supporting IQOS as a smoking cessation aid or harm reduction tool
4. Cautioned on the likelihood of dual use and the risks associated with dual use
5. Advised to either quit using IQOS or quit smoking cigarettes if they are using both
6. Referred to a smoking cessation program if interested in quitting smoking

CONFIDENTIAL

This material is the property of the University of Pennsylvania. Do not disclose or use except as authorized in writing by the study sponsor

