associated with dual use; (3) advised to either quit using IQOS or to quit smoking cigarettes if they are using both; and (4) referred to a smoking cessation program if interested in quitting smoking. The **primary outcome** measure will be the longitudinal daily count of cigarettes from baseline to the end of the 14-day IQOS switch phase. Changes in motivation to quit smoking from baseline to study end will be a **secondary outcome**.

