2. Any medical condition, illness, disorder, adverse event (AE), or concomitant medication that could compromise participant safety or significantly impact study performance as determined by the Principal Investigator. Subjects may be deemed ineligible for any of the aforementioned reasons at any point throughout the study, as well as during the initial telephone screen.
3. Significant non-compliance with protocol and/or study design as determined by the Principal Investigator and/o. Subjects may be deemed ineligible at any point throughout the study.

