5.7 Early Withdrawal of Subjects

5.7.1 When and How to Withdraw Subjects

[figure not shown]
Participants are free to withdraw from the study on their own accord at any time. In addition, participants may be withdrawn by the Principal Investigator at any time per the exclusion criteria listed previously. No follow-up data collection is required for participants who withdraw or are deemed ineligible throughout the study.

6. Study-Provided IQOS Device and HeatSticks

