Cigarette Smoking and IQOS use: Although cigarette smoking is associated with many diseases, we do not believe the risk is beyond every day risk as all participants must be current cigarette smokers to be eligible. We will inform participants that cigarette smoking has been shown to cause diseases such as emphysema and cancer. There will be a phase of the study where participants will be instructed to switch completely to IQOS. If participants don't completely switch from smoking cigarettes to using IQOS, their risks from smoking will remain the same.

Important safety information regarding IQOS: IQOS works exclusively with HeatSticks. Never use IQOS with a cigarette or any other tobacco sticks or accessories. Do not remove a tobacco stick (HeatStick) while in use. Tobacco sticks (HeatSticks) are single use only and should never be reused. Tobacco sticks (HeatSticks) should never be lit with a match, lighter, or any other flame source. **Keep tobacco sticks out of reach of children and pets.** If tobacco sticks are swallowed, seek medical attention immediately due to risk of nicotine ingestion. **Store your tobacco sticks in a cool, dry place.** Do not expose product to high humidity conditions or direct sunlight. Do not use IQOS during hot conditions or in periods of high humidity. **Pay attention to signs that your battery may be leaking.** The IQOS Holder and Pocket Charger are powered with sealed Lithium-ion batteries. Under normal conditions of use, the battery is sealed. If you notice fluid leaking from the battery, follow these precautions, discontinue using the product immediately and contact *[name]* at [contact], or *[name]* at [contact]. In case of contact with skin, wash hands and do not touch eyes. In case of contact with eyes, immediately flush with running water for at least 15 minutes and seek medical attention. If fluid is inhaled, get fresh air and seek medical attention. If you swallow fluid, seek medical attention immediately. Do not induce vomiting or ingest food or drink. **Stop using IQOS and seek medical attention immediately if you experience any symptoms that may indicate a serious allergic reaction:** swelling of the face, lips, tongue, gums, throat, or body; difficulty breathing, or wheezing.

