12.1 Informed Consent

A fully trained staff member will obtain informed consent using the combined consent and HIPAA form approved by the IRB (UPENN). The consent process will take place prior to the initiation of any study procedures. The consent process will occur electronically via REDCap OR in person at the CIRNA and will involve a discussion of the study requirements and procedures. During in-person consent, the combined consent and HIPAA form will be read verbatim to participants.

CONFIDENTIAL

This material is the property of the University of Pennsylvania. Do not disclose or use except as authorized in writing by the study sponsor

During electronic consent, the combined consent and HIPAA form will be completed virtually via REDCap. Participants will be required to read the entire consent in order to participate in the research study. Participants will have an opportunity to ask any questions and/or express concerns. Participants can elect not to participate and may withdraw at any time without penalty. Participants will receive a copy of the combined consent and HIPAA form for their records. In addition, participants will be given the Principal Investigator's contact information (located on pg.1 of the consent) should they wish to speak to the Investigator during the course of the study regarding their consent or the study procedures. The consent process will take place in English, there will be no waiting period, no coercion to participate, and all participants will be considered competent to provide informed consent (i.e., they will be asked if they understand what they are consenting for). The consent form must be signed and dated by the participant and the investigator-designated research professional obtaining the consent. The original signed combined consent and HIPAA form will be centrally stored in regulatory binders (consent).

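### The dual-use caution, quit-one-product advice and cessation referral are scheduled only on Day 22, so a participant who leaves after receiving the device has no scheduled exit delivery of them

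*Combined protocol and SAP*

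**What the plan says.** The device and the first 7-day HeatStick supply are handed over on Day 7 (7.2.4). At that visit participants are to "Be provided with instructions to switch completely from smoking combustible cigarettes to using IQOS".

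The four closing messages are items 3 to 6 of the Day 22 visit (7.2.9). They are the lack-of-evidence statement, the dual-use warning ("Cautioned on the likelihood of dual use and the risks associated with dual use"), the advice to drop one product, and the referral to a cessation program for those interested. Section 4.1 gives the same list for the same day, with participants "advised to either quit using IQOS or to quit smoking cigarettes if they are using both".

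On leaving early, 5.7.1 lets participants withdraw whenever they wish and adds that "participants may be withdrawn by the Principal Investigator at any time per the exclusion criteria listed previously". The general exclusions in 5.4 include significant non-compliance, with the note that "Subjects may be deemed ineligible at any point throughout the study". For those who leave, 5.7.1 says: "No follow-up data collection is required for participants who withdraw or are deemed ineligible throughout the study".

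Two other places bear on the point. Section 8.1 states that for participants who do not switch completely, "their risks from smoking will remain the same". Section 12.1 says that at in-person consent "the combined consent and HIPAA form will be read verbatim to participants"; electronic consent also requires the whole form to be read.

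**The concern.** The study puts a new nicotine product into the hands of smokers, and its own analytic plan (7.5) expects most of them to have some level of dual use. The protocol answers this with a closing conversation, but ties that conversation to one visit, 15 days after the device is handed over. Anyone who leaves in between falls outside the schedule.

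Early leavers may be dual users too. Every participant must report interest in quitting within 6 months (5.3), so the referral is relevant to all of them. The study's own hypothesis H1c is that IQOS use lowers motivation to quit. If that is right, a person who has used the device and then left is someone for whom the advice and referral matter.

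What is at stake is participant protection. The estimates are not affected.

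**Working it through.** The plan states no figure on this point, so the check is a reading of the schedule, followed by a range for the number affected.

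**Where the four messages appear**

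| Visit | Section | Any of the four messages listed? |
|---|---|---|
| Intake | 7.2.2 | No |
| Day 6 | 7.2.3 | No |
| Day 7 (device handed over) | 7.2.4 | No |
| Days 11, 14, 17, 21 | 7.2.5 to 7.2.8 | No |
| Day 22 | 7.2.9, items 3 to 6 | All four |

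Section 4.1 also assigns all four to Day 22. The interval from handover is 22 − 7 = 15 days, with four visits in between and none of the messages listed at any of them.

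**What happens on early exit**

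- Section 5.7.1 describes no exit visit, call, debrief or referral. It waives data collection; it does not prohibit contact.
- The only advice tied to withdrawal is in 8.1, for a participant who becomes pregnant: a recommendation to consult an obstetrician or maternal-fetal specialist.
- Adverse-event follow-up (9.1, 9.2.2) may bring staff into contact with a leaver, but it carries none of the four messages.

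**How many could be affected**

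Let *d* be the share of device recipients who do not complete Day 22. The documents give no value, so 5%, 10% and 20% are assumptions. The total of 160 comes from 4.1 and 4.2. Section 4.2 presents it as the number completing, so both readings are shown.

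- If 160 receive a device, the number missing Day 22 is 160 × *d*.
- If 160 complete, the number missing Day 22 is 160 × *d* / (1 − *d*).

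| Assumed *d* | 160 receive a device | 160 complete |
|---|---|---|
| 5% | 160 × 0.05 = 8 | 160 × 0.05 / 0.95 = 8.4 |
| 10% | 160 × 0.10 = 16 | 160 × 0.10 / 0.90 = 17.8 |
| 20% | 160 × 0.20 = 32 | 160 × 0.20 / 0.80 = 40.0 |

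These counts cover all non-completers. The advice to give up one product applies only to those using both, so fewer people would miss that item.

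**The case against.** The best reply is that this argues from silence while the documents that could settle it are out of view. The consent form was not available for this review. It is gone through in full before any procedure and is a natural home for the lack-of-evidence statement and the dual-use warning. Staff also work from a manual of procedures and SOPs (8.3.1, 11.2), where exit handling could sit. Nothing in 5.7.1 stops staff from giving a leaver the referral.

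The visible text also overlaps with the messages. The Day 7 instruction to switch completely is, in substance, one of the two options in the Day 22 advice. Section 8.1 covers part of the dual-use risk. Section 8.2 presents whether IQOS can replace cigarettes or weakens motivation to quit as open questions. A missed Day 22 may be rescheduled (8.3.1 mentions follow-up of such participants), and attending it earns a $55 bonus (Table 2).

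Much of this stands. Some of the content may well reach participants earlier, and only those who still do not complete Day 22 are affected. But none of the visible text provides the cessation referral, the option of giving up IQOS, or the lack-of-evidence statement at exit. The advice for people using both products also depends on a status that arises only after the device is in use, so consent at Intake is a poor substitute. Leaving delivery to staff discretion is weaker than scheduling it, and the documents give no reason to treat leavers differently from completers.

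**Conclusion.** The concern holds as a minor point of participant protection. Followed as written, the schedule gives completers four messages that early leavers have no scheduled occasion to receive at exit.

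The size is uncertain: 8 to 40 people over the assumed range of 5% to 20% non-completion. The conclusion does not depend on that range.

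The consequence is limited. Leavers were already smokers, HeatSticks come in 7-day supplies (6.2), and unused sticks are collected at all visits (6.3). No endpoint, sample size or inference changes. Confidence is medium, because the consent form and procedures manual could not be checked and may supply part of the content.

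**What to change.** Amend 5.7.1 so that every participant who has received a device and will not complete Day 22, after any attempt to reschedule, is offered items 3 to 6 of 7.2.9 at last contact, by visit, phone or letter. At the same contact, ask for the return of any unused HeatSticks not already collected under 6.3.

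Leave the Day 22 timing unchanged for completers, with the messages after the Contemplation Ladder, so that they cannot influence the motivation outcome. Leave the Day 11 to 21 visits as they are.

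The cost is the amendment wording and one contact per early leaver. Phone, email and text are already used for visit reminders (7.2.1). Some leavers will be unreachable, so the gap is only partly closed. No assessment is added and outcome data are unaffected.

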7.3 Table 1. Study Measures and Time Points

Table 1. Measures		Bio-behavioral Laboratory Visits							
Description of Time Point		Intake			Days 8-21: Switch to IQOS				End of study
Day #		Day 0	Day 6	Day 7	Day 11	Day 14	Day 17	Day 21	Day 22
Demographic & Baseline Covariates									
Demographics	X								
Smoking History	X								
Nicotine Dependence	X								
Cigarettes per day (days 1-5)		X							
CO	X	X	X	X	X	X	X		
Predictor Variables									
Craving Relief		X							
Withdrawal Relief		X							
Subjective Reward of IQOS		X							
IQOS Risk Perceptions		X							
Relative Reinforcing Value of IQOS			X						
IQOS sticks per day				X	X	X	X	X	
Outcome Variables									
Cigarettes per day				X	X	X	X	X	
Quitting Motivation	X								X

CONFIDENTIAL

This material is the property of the University of Pennsylvania. Do not disclose or use except as authorized in writing by the study sponsor

7.4 Description of Study Measures

7.4.1 Screening/Covariates

Urine Drug Screen: A urine sample (~20-30ml) will be collected at the Intake Visit to conduct a urine drug screen. The urine drug screen indicates whether the subject has recently taken any of the following recreational drugs or medications: THC, cocaine, opiates, amphetamines, methamphetamines, phencyclidine (PCP), ecstasy (MDMA), barbiturates, benzodiazepines, methadone, tricyclic antidepressants, and/or oxycodone. Participants with a positive urine drug screen for any substance listed above other than THC or tricyclic antidepressants will be deemed ineligible. A urine sample that doesn't register a temperature reading of at least 90 degrees Fahrenheit will not be considered a valid sample. In an effort to remain CLIA-compliant, results from urine drug screen will not be shared with participants. Participants will be informed that the testing is for research purposes only and that they will be informed of their eligibility status, but not of the specific testing results. In order to document inclusion/exclusion criteria for regulatory purposes, results of the urine drug screens (test cup) will be retained in research charts and in an electronic research record within our local data management system (Access). These results are not and will not be entered into a participant's electronic medical record.

Urine Pregnancy Test: At the Intake Visit, female participants will be supplied with a simple, CLIA-waived hCG pregnancy test strip and a urine sample cup. Female participants will be informed that pregnant women are not advised to participate in this research study. Participants will then be instructed to self-administer the pregnancy test and inform the study staff if they would like to continue participation after they have reviewed the results of the pregnancy test. Participants will be informed that there is no penalty for discontinuing participation at this point in the visit and that they will still receive travel reimbursement for the visit.

Breath Alcohol Concentration (BrAC): Participants will complete a BrAC assessment at the Intake Visit. Participants will be made aware of the BrAC assessment prior to the visit and asked to avoid alcohol and alcohol-based products (e.g. mouthwash, breath spray, etc.) the evening and morning before the Intake Visit. The BrAC monitor is a handheld device that uses a disposable mouthpiece and reports the concentration of alcohol in exhaled breath. Any reading greater than 0.000 indicates alcohol consumption within the last 14 hours. Participants with a BrAC greater than 0.000 at the Intake Visit will be deemed ineligible.

Medical History Form: A medical history form (led by the research staff) will be completed to review for applicable contraindications previously listed under Key Inclusion/Exclusion Criteria at the Intake Visit.

Demographics and Smoking History (FTND): Standard surveys will collect demographics information such as age, sex, race, ethnicity, education level, and income [7,10,12]. Standard survey questions will assess smoking history (e.g., age at initiation, current smoking rate). Nicotine dependence will be assessed with the Fagerstrom Test for Nicotine Dependence (FTND). This 6-item measure has good internal consistency ($\alpha = .64$) and high test-retest reliability ($r = .88$) [44].

Smoking Urges/Craving (QSU-B): The well-validated and reliable 10-item brief Questionnaire of Smoking Urges will assess craving for cigarettes. The QSU-B utilizes a "right now" frame of reference.

Adverse Events Form (Open-Ended AEs): Participants will be asked an open-ended question about any symptom or medical event that may be related to their study participation. These events will be documented as **unanticipated (unexpected)** AEs unless they are otherwise outlined in the protocol and/or consent form (i.e. related to withdrawal, assessments, etc.). The reporting period for each

CONFIDENTIAL

This material is the property of the University of Pennsylvania. Do not disclose or use except as authorized in writing by the study sponsor

assessment will inquire about any event(s) or symptom(s) experienced since the last in-person visit. If a participant reports a symptom or medical event, they will be asked to rate the severity of the event utilizing the following severity scale: 0 (None=No Concerns), 1 (Mild=Issue does not interfere with usual daily activities), 2 (Moderate=Issue does interfere with some activities), and 3 (Severe=No normal activities are possible). See section 8.2.1: AE Collection Methods for further details.

Carbon Monoxide (CO) will be measured using a Vitograph CO monitor (Lenexa, KS). A CO > 5 is indicative of combustible cigarette smoking [25,45,46]. HNB products are expected to result in significantly lower increases in CO compared to a combustible cigarettes [47]. Five minutes of IQOS use did not result in clinically significant increases in CO (0.3 ppm) after overnight abstinence compared to five minutes of combustible cigarette [27]. We will include CO as a covariate in our statistical models.

Concomitant Medications: At the Intake Visit, participants will be asked to list all medications (prescription or non-prescription) and NRTs currently taken and/or recently discontinued (within the past 14 days) as a baseline collection. All information will be collected on a Concomitant Medication Log that will be maintained within the participant's study chart. At every subsequent in-person visit, participants will be asked if they have taken any additional medications (prescription or non-prescription), NRTs, and/or changed the dosage or stopped taking any previously reported medications since their last in-person visit. Participants who report taking contraindicated medication(s) over the course of the study period may only remain eligible if the Principal Investigator determine that the contraindicated medication(s) did not impact the study design, data quality, and/or participant safety and welfare.

